- a. Women with gestational diabetes will be contacted prior to their appointment by either phone or letter to remind them to come to their post-partum visit prepared for the fasting, 2-hour, 75-g glucose tolerance test.
- b. Women diagnosed with gestational diabetes will undergo a 2-hour, 75-g glucose tolerance test at the time of their post-partum visit at OBCC or resident continuity clinic. They will receive \$10 for undergoing this testing.
- c. All women will be asked whether they or their infant have been re-admitted to the hospital since the time of discharge and the reason for admission. Permission will be obtained to request records for re-admission diagnoses.

7. Outcome Measures

The primary outcome will be a composite outcome of macrosomia (birth weight >4000g), primary cesarean, gestational hypertension or preeclampsia, shoulder dystocia, neonatal hyperbilirubinemia, and neonatal hypoglycemia. Each of these outcomes will also be evaluated individually as secondary outcomes. Additional secondary outcomes will include premature delivery (<37wks).

- a. Macrosomia: Will be defined by measurement of infant birth weight. Macrosomia is a birth weight >4000 g.
- b. Primary cesarean: A primary cesarean delivery for any indication will be considered as having the outcome of interest.
- c. Gestational hypertension: Defined by systolic blood pressure ≥ 140 or diastolic blood pressure ≥ 90 without proteinuria (urine protein/creatinine ratio < 0.19 or 24-hour urine protein < 300 mg).
- d. Preeclampsia: Defined by systolic blood pressure ≥ 140 or diastolic blood pressure ≥ 90 with proteinuria (urine protein/creatinine ratio ≥ 0.19 or 24-hour urine protein ≥ 300 mg). Preeclampsia diagnosis will also be refined by mild or severe. Severe preeclampsia will be defined as systolic blood pressure ≥ 160 , diastolic blood pressure ≥ 110 , proteinuria ≥ 5000 mg in 24 hours or 3+ urine dip, platelets < 150 , AST > 60 , oliguria (< 500 mL urine/ 24 hours), pulmonary edema, creatinine > 1.0 .
- e. Shoulder dystocia: As documented by delivering physician; defined as requiring more than routine downward traction to achieve delivery of anterior shoulder. The length of the shoulder dystocia and maneuvers required to relieve the shoulder dystocia will be documented.

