- f. Neonatal hyperbilirubinemia: Neonatal bilirubin levels will be recorded. Hyperbilirubinemia will be defined $> 95^{\text{th}}$ percentile gestational age and hour of life. The treatment of hyperbilirubinemia (i.e. phototherapy) will also be recorded.
- g. Neonatal hypoglycemia. Blood sugar levels will be abstracted from neonatal charts. Neonatal hypoglycemia will be defined as blood sugar < 35 mg/dL.

8. Data Collection Form Definitions

- a. Randomization Form
 - i. Age at the time of presentation
 - ii. Body mass index as defined by self-reported pre-pregnancy weight & measured height
 - iii. Gestational age <20 weeks, 0 days as defined by earliest documented ultrasound
 - iv. Known history of diabetes mellitus by patient report or as documented in clinical records
 - v. Major medical illness
 - 1. Chronic/daily prednisone use
 - 2. On home oxygen
 - 3. Prior cardiac surgery
 - 4. History of cardiomyopathy, valvular stenosis, pulmonary hypertension
 - 5. History of any transplanted organ
 - 6. HIV/AIDS
 - 7. Hemoglobinopathy (i.e. sickle cell disease)

Conditions not considered a major medical illness:

 - 1. Chronic hypertension
 - 2. Asthma (unless requiring prednisone on daily basis)
 - 3. Obstructive sleep apnea (unless requiring home oxygen)
 - vi. Unable to provide informed consent
 - 1. Language barrier
 - 2. Prisoner
 - 3. Mental illness
 - 4. Judgment of person performing enrollment
 - vii. Known fetal anomalies
 - 1. Structural anomalies (heart defect, brain defect, renal anomaly, abdominal wall defect) or known fetal aneuploidy by karyotype or non-invasive prenatal diagnosis
 - 2. Soft markers of aneuploidy are not exclusion criteria (echogenic intracardiac focus, choroid plexus cyst, renal pelvis dilation/pyelectasis)
 - viii. History of bariatric surgery
 - 1. Either banding procedure or Roux-en-Y
 - ix. Multifetal gestation
 - x. Prior cesarean
- b. Enrollment Form
 - i. Measured height without shoes

- ii. Self-reported pregnancy weight obtained from patient interview at time of enrollment
 - iii. History may be obtained from patient directly or from chart
 - iv. Exam at time of enrollment
- c. Diabetes Testing Form
 - i. Document Randomization group
 - ii. Document date and value of BSST, GTT, HbA1c, and Glycomark
- d. Prenatal Care Data Collection Form
 - i. Document whether exclusion criteria developed during course of prenatal care
 - ii. Record number of prenatal visits and date, weight, and blood pressure each visit.

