### 3. PRIMARY HYPOTHESIS

#### 3.1. Primary Hypothesis #1: Impact of Early GDM Screening on the Primary Outcome (a Composite of Key Perinatal Outcomes)

*H0: There will be no difference in the rate of the primary outcome (quantified by the composite outcome of key perinatal outcomes) in EGGO participants randomized to the Early screening group compared to participants randomized to the Routine screening Group.*

**3.1.1. Primary Outcome:** The primary outcome is a composite of the following items: macrosomia, primary cesarean, pregnancy induced hypertension (gestational hypertension or preeclampsia), shoulder dystocia, neonatal hyperbilirubinemia, and neonatal hypoglycemia. The occurrence of 1 or more of these items will be considered an occurrence of the primary study outcome. Individual definitions of these outcomes are listed below.

- a. Macrosomia: Will be defined by measurement of infant birth weight. Macrosomia is a birth weight >4000 g.
- b. Primary cesarean: A primary cesarean delivery for any indication will be considered as having the outcome of interest.
- c. Gestational hypertension: Defined by systolic blood pressure  $\geq 140$  or diastolic blood pressure  $\geq 90$  without proteinuria (urine protein/creatinine ratio  $< 0.19$  or mg).
- d. Preeclampsia: Defined by systolic blood pressure  $\geq 140$  or diastolic blood pressure  $\geq 90$  with proteinuria (urine protein/creatinine ratio  $\geq 0.30$ ). Preeclampsia diagnosis will also be refined by mild or severe. Severe preeclampsia will be defined as systolic blood pressure  $\geq 160$ , diastolic blood pressure  $\geq 110$ , platelets  $< 100$ , AST  $> 80$  serum creatinine  $> 1.2$ .
- e. Shoulder dystocia: As documented by delivering physician; defined as requiring more than routine downward traction to achieve delivery of anterior shoulder. The length of the shoulder dystocia and maneuvers required to relieve the shoulder dystocia will be documented.
- f. Neonatal hyperbilirubinemia: Neonatal bilirubin levels will be recorded. Hyperbilirubinemia will be defined  $> 95$ th percentile gestational age and hour of life. The treatment of hyperbilirubinemia (i.e. phototherapy) will also be recorded.
- g. Neonatal hypoglycemia. Blood sugar levels will be abstracted from neonatal charts. Neonatal hypoglycemia will be defined as blood sugar  $< 35$ mg/dL.

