**3.1.2. Analysis Plan:** This hypothesis effect of Early versus Routine GDM screening in obese pregnant women. The  $\chi^2$  test of association will be used to evaluate whether the rate of the primary outcome differs between the treatment groups. The primary analysis will be an intention-to-treat analysis of all individuals randomized to the two treatment groups, regardless of whether evaluation plans were followed. Risk ratios (RR) and 95% confidence intervals (CIs) will be computed and presented.

Standard comparison of the covariate characteristics at baseline between study groups will be undertaken (Section 2) to assess the randomization balance on measured covariates. Tests of significance will be two-sided and evaluated at the 0.05 level of significance. Since the sample size for EGGO is large, it is unlikely that “important” covariates (such as race, BMI or age) will be imbalanced through the

randomization process. Further, randomization is stratified by BMI (BMI <40 and BMI ≥40) and site (UAB and Oschsner).

In the unlikely event that imbalance occurs, adjustment for covariates will be made by modeling the log-odds of the outcome using multivariable logistic regression including terms indicating group membership and each of the imbalanced covariates. In other words, the log-odds of the primary outcome for any individual will be modeled using the following form:

$$\ln\left(\frac{P(\text{outcome})}{1-P(\text{outcome})}\right) = \beta_0 + \beta_1 x_1 + \sum \beta_j z_j.$$

Above,  $x_1 = 1$  if the patient is in the Early group and equals 0 if the patient is in the Routine group. The set of  $z_j$ 's consists of all covariates in the model including site. Hence, under this model, the term  $\beta_1$  represents the difference in the log-odds between the two groups. To address the hypothesis of interest for primary hypothesis #1, we will perform a statistical test of  $H_0: \beta_1 = 0$  vs.  $H_1: \beta_1 \neq 0$ . Quantification of the treatment effect will be performed by exponentiation of the estimated coefficient,  $\exp(\beta_1)$ , to obtain an estimate of the odds ratio. The confidence interval will be determined similarly.

The stratification by BMI and by site allows for the investigation of differential effects across sites and across BMI thresholds. The presence of a homogeneous effect across center and across BMI thresholds will be examined using the Breslow-Day test.

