**3.1.3. Sample Size for Primary Outcome:** Based on prior studies performed at UAB, the incidence of macrosomia, cesarean delivery, shoulder dystocia, and preeclampsia in obese women with gestational diabetes was 56%. Using a conservative estimate of these outcomes as 50%, to detect a 50% reduction in the incidence of adverse outcomes ( $\alpha=0.05$ ,  $\beta=0.80$ ), 58 gestational diabetics per group are necessary.

The diagnosis of GDM will occur after patients in this study have been screened for GDM. As a result, a large number of patients must be randomized to each diagnostic procedure in order to achieve 58 gestational diabetics in each group. Prior reports of the incidence of GDM are between 6-20% depending on ethnicity and the screening and diagnostic criteria used. Using an incidence of 10% GDM in obese women, 580 subjects per screening group are necessary. Approximately 3,100 women per year attend the UAB clinic for obstetric visits, and approximately 40% of these women are obese. Assuming a 50% acceptance of enrollment, we anticipate enrolling 620 women per year. Therefore, we feel that we can enroll 1,160 subjects in 3 years.

**3.2. Interim Monitoring:** One interim analysis, evaluating both efficacy and futility, will be conducted after 600 women have completed the study (300 in each group have delivered). Under the assumption that 10% of obese women have GDM, we expect to have approximately 30 gestational diabetics in each group. Using an O'Brien-Fleming alpha spending function and one interim analysis, we will use the following critical stopping values:

At the interim look:     If  $\chi^2 > 7.82$  (i.e.  $p < 0.005$ ) then reject  $H_0$  and consider stopping the trial;  
                                  Otherwise, continue.

At the final look:        If  $\chi^2 > 3.91$  (i.e.  $p < 0.048$ ) then reject  $H_0$ .

We do not propose a formal stopping rule for safety or futility, but note that the DSMB will be presented with safety data and information on study progress. In addition, we note that the overall sample size of 58 gestational diabetics per group will provide 80% power for the hypothesized effect size using a modified alpha level of 0.048 at the final analysis. Conditional power estimates may be provided to assist the DSMB in their evaluation of efficacy and futility.

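### The sample size for the primary outcome uses an event rate for four outcomes; the primary composite adds three more, so 58 per group and 80% power are not shown to apply to it

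*SAP*

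**What the plan says.** SAP 3.1.3, headed as the sample size for the primary outcome, has one source for its event rate, prior studies at the lead site: "the incidence of macrosomia, cesarean delivery, shoulder dystocia, and preeclampsia in obese women with gestational diabetes was 56" percent. It continues: "Using a conservative estimate of these outcomes as 50%, to detect a 50% reduction in the incidence of adverse outcomes". With alpha 0.05 and 0.80 (printed as beta, evidently meaning power), it requires 58 women with GDM per group. SAP 3.2 adds that this number "will provide 80% power for the hypothesized effect size using a modified alpha level of 0.048 at the final analysis".

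The composite in SAP 3.1.1 consists of "macrosomia, primary cesarean, pregnancy induced hypertension (gestational hypertension or preeclampsia), shoulder dystocia, neonatal hyperbilirubinemia, and neonatal hypoglycemia", and any one of these counts as an event. Protocol section 7 has the same components. The Randomization Form in Protocol section 8.a lists "Prior cesarean" as an item. SAP 3.1.2 states: "Tests of significance will be two-sided and evaluated at the 0.05 level of significance".

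**The concern.** The two event lists differ. Three components of the composite (gestational hypertension, neonatal hyperbilirubinemia and neonatal hypoglycemia) are absent from the set behind the 56%. The composite also specifies primary cesarean, whereas the planning sentence refers to cesarean delivery without qualification and does not say whether repeat cesareans were counted.

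Two inputs are therefore unsupported for the actual endpoint: the control rate, and the assumption that early screening halves it. The second matters at least as much as the first. Adding events to a composite raises its rate, but this helps power only if the added events also respond to the intervention. If they do not, they dilute the relative effect. At stake is whether the stated power describes the trial's endpoint at all.

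**Working it through.** **Inputs from the documents.** Four-event rate 56%, planning rate 50%, relative reduction 50%, 58 women with GDM per group (SAP 3.1.3); two-sided tests (SAP 3.1.2); final-look alpha 0.048 (SAP 3.2). Every composite rate and added-event rate below is an assumption, because the documents give none.

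**Formulas.** Two proportions, pooled variance under the null, no continuity correction, with p̄ = (p1 + p2)/2:

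- n per group = [z(α/2)·√(2p̄(1−p̄)) + z(power)·√(p1(1−p1) + p2(1−p2))]² / (p1−p2)²
- power = Φ{ [|p1−p2|·√n − z(α/2)·√(2p̄(1−p̄))] / √(p1(1−p1) + p2(1−p2)) }

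The z values are 1.960 for alpha 0.05, 1.977 for alpha 0.048 and 0.842 for 80% power.

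**Step 1: the plan's own figure.** For 50% vs 25%, p̄ = 0.375 and the two square roots are 0.6847 and 0.6614.

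- n = (1.960 × 0.6847 + 0.842 × 0.6614)² / 0.25² = 57.7, so 58. The stated number is reproduced.
- Power with 58 per group is 80.2% at alpha 0.05 and 79.7% at alpha 0.048, so the stated 80% is also reproduced.
- At the unreduced rate, 56% vs 28%, n would be 48. Lowering 56% to 50% is therefore conservative for the four events.

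**Step 2: the whole composite is halved.** Here the added events raise the control rate and respond as strongly as the original four. With 58 per group and alpha 0.048:

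| Assumed composite rates | Power |
|---|---|
| 55% vs 27.5% | 86% |
| 60% vs 30% | 91% |
| 70% vs 35% | 97% |

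**Step 3: the added events do not respond.** Let the four events fall from 50% to 25%, and let the added events occur independently at rate q in both groups. Then control = 1 − 0.50(1−q) and early = 1 − 0.75(1−q).

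| Assumed q | Control vs early | Ratio | Power, 58 per group, alpha 0.048 | n per group for 80%, alpha 0.05 |
|---|---|---|---|---|
| 10% | 55% vs 32.5% | 0.59 | 68% | 76 |
| 20% | 60% vs 40% | 0.67 | 57% | 97 |
| 30% | 65% vs 47.5% | 0.73 | 47% | 125 |

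**Step 4: comparison.** A 60% composite control rate appears in both tables, with 91% power in one and 57% in the other. The control rate alone does not settle the power; the assumed effect on the added events is needed as well.

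**The case against.** The best defence is that nothing has been miscalculated. The figure of 58 follows from its inputs, and the gap affects neither the type I error, nor the endpoint definition, nor the analysis. That is correct: this is an unsupported planning input, not an arithmetic error.

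Three stronger readings are tempting, and the documents do not support them.

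- *That 50% is not conservative.* The sentence applies the word to the outcomes it has just named, and for those it is right (58 rather than 48 per group). The SAP does not claim that 50% is conservative for the six-item composite.
- *That the source counted any cesarean, so the composite rate must be lower.* Cesarean is unqualified in 3.1.3, and the eligibility and definitions of the source studies are not given. They may have counted only primary cesareans. The prior-cesarean item on the Randomization Form concerns this trial, not those studies. The three missing components carry the point without this inference.
- *That the trial is underpowered for its composite, or that the extra components can only help.* Steps 2 and 3 show that either is possible.

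It can also be said that the event set is not the main weakness of the power statement, because SAP 3.1.2 analyses all randomized women while 3.1.3 powers a comparison among women with GDM, about 10% of them. That is a fair and separate point. It does not remove this one: a calculation for all randomized women would also need a rate for the correct composite.

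**Conclusion.** The point holds. The 58 per group and 80% power belong to a four-event set. The documents give no rate for the composite in SAP 3.1.1, no bridge from one to the other, and no basis for applying the 50% reduction to gestational hypertension, neonatal hyperbilirubinemia and neonatal hypoglycemia.

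Under the assumptions shown, power with 58 women with GDM per group runs from 47% (added events at 30%, not responding) to 97% (a 70% composite, fully halved), against the stated 80%. These are illustrations, not estimates. The non-responding cases also assume that the added events are independent of the original four. The range shows that the gap is material; its direction cannot be determined from the documents.

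**What to change.** In SAP 3.1.3, restate the control rate and the assumed treatment effect for the exact composite of 3.1.1, and say how cesarean was counted in the source. Use the prior local data if they hold all the components; the documents do not say whether neonatal bilirubin and glucose were recorded. If they were not, give an assumed range for the composite rate and for the response of the added events, with the power at each. Restate power for the planned sample size; this is not a proposal to enrol more women. State that the conservative estimate refers only to the four-event rate.

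The cost is at most one re-tabulation of existing data plus SAP wording. The downside is that the stated power may fall. The change corrects the event set only. Because the primary analysis covers all randomized women, the restated figure would still not be the power of the planned test until that is dealt with separately.

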 - iii. In those who are not diagnosed with GDM at the early screen, repeat testing will be performed at 24-28 weeks.
 - b. **Routine Screening Group.**
 - i. Women assigned to routine screening will have a blood draw for HbA1c and Glycomark between 14 weeks, 0 days and 20 weeks, 0 days gestation.

- If HbA1c $\geq 6.3\%$ in the routine screening group, the result will be unblinded and the clinician informed. These women will subsequently enter into routine GDM care with dietary counseling and patterned blood sugars.
 - If the patient is between 14 weeks, 0 days and 20 weeks, 0 days this blood draw may be performed at the enrollment visit. Otherwise, may be done in clinic with routine prenatal labs.
- ii. Women assigned to “routine screening” will undergo the 1-hour, 50-g glucose load (BSST) between 24 weeks, 0 days and 28 weeks, 0 days gestation. At the time of the BSST, a purple & gold top tube for HbA1c & Glycomark will be drawn (see baseline procedures below).

4. Results of Glucose screening tests

- a. Women whose BSST is ≥ 135 mg/dL, will be scheduled to undergo diagnostic testing with a 3-hour GTT (100-g glucose load). The currently used criteria to diagnose GDM (Carpenter Coustan criteria) will be used to diagnose GDM. By these criteria, a woman must have 2 elevated blood sugar values at either of the following timepoints and values:
1. Fasting ≥ 95 mg/dL
 2. 1-hour ≥ 180 mg/dL
 3. 2-hour ≥ 155 mg/dL
 4. 3-hour ≥ 140 mg/dL
- b. The attending physician will review the three-hour GTT results to confirm the diagnosis of GDM.
- c. Women who have a BSST > 200 will have a fasting blood sugar checked prior to undergoing a 3-hour GTT. If the fasting blood sugar < 126 mg/dL, the patient will proceed with a 3-hour GTT. If the fasting blood sugar ≥ 126 mg/dL, the diagnosis of GDM will be made.
- d. Women who are not diagnosed with GDM between 14-20 weeks (i.e. women who have a normal 1-hour BSST or who have an elevated 1-hour BSST but a normal 3-hour GTT) will repeat the 1-hour BSST at 24-28 weeks. At the time of the repeat BSST, a purple & red top tube for HbA1c & Glycomark will be drawn (see baseline procedures below).
- i. Women who are diagnosed with GDM will enter into routine GDM care with dietary counseling and patterned blood sugars. A purple & gold top tube for HbA1c & Glycomark will be drawn between 24-28 weeks, and 0 days gestation (see baseline procedures below).

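### The stated 80% power is for 58 versus 58 women with GDM, but the primary test compares all 1,160 randomized women; if the effect is confined to GDM, its power at the planned 10% incidence is well below 80%

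*SAP*

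**What the plan says.** SAP section 3.1.3 starts from earlier data in which "the incidence of macrosomia, cesarean delivery, shoulder dystocia, and preeclampsia in obese women with gestational diabetes was 56" percent. It rounds this down to 50%, assumes early screening halves it, and obtains 58 women with GDM per group. It then scales up to the number randomized: "Using an incidence of 10% GDM in obese women, 580 subjects per screening group are necessary". Section 3.2 returns to the same basis for the final look: "the overall sample size of 58 gestational diabetics per group will provide 80% power for the hypothesized effect size" at a modified alpha of 0.048. It also describes the interim look by the expected number of women with GDM, about 30 per group.

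The primary hypothesis in section 3.1 compares the composite rate between participants as randomized. Section 3.1.2 sets the test as a chi-square and the population in these words: "The primary analysis will be an intention-to-treat analysis of all individuals randomized to the two treatment groups". No primary test restricted to women with GDM is specified. Neither document gives an event rate for women without GDM, an overall event rate, or power for the all-randomized comparison.

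**The concern.** The sample size is justified by one comparison and the trial is decided by another. About 90% of the women in the primary test are expected not to have GDM. Under Protocol section 4 (results of glucose screening tests), women not diagnosed continue ordinary prenatal care, so there is little reason to expect an effect among them. They add events to both arms and dilute the difference.

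The planning rate also belongs to a narrower endpoint. It covers macrosomia, cesarean, shoulder dystocia and preeclampsia, whereas the trial composite includes "pregnancy induced hypertension (gestational hypertension or preeclampsia), shoulder dystocia, neonatal hyperbilirubinemia, and neonatal hypoglycemia". Gestational hypertension and the two neonatal items were therefore not in the 56%.

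A non-significant result would be read as coming from a trial with 80% power, when it might say little about benefit in women with GDM. Section 3.2 also allows conditional power to be shown to the DSMB without saying which effect it assumes, so the mismatch could reach a stopping discussion.

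**Working it through.** **Inputs from the SAP.** Women with GDM: 50% routine, 25% early. GDM incidence g = 10%, with a wider range given as "Prior reports of the incidence of GDM are between 6-20% depending on ethnicity". 580 women per arm. Two-sided alpha 0.05, or 0.048 at the final look (chi-square above 3.91).

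**Assumed here.** The composite rate q in women without GDM is not in the documents; 20-50% is used as the main range, with lower values shown. It is taken as equal in both arms (no effect without GDM), and g is the same in both arms.

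**Formula.** Two proportions, pooled variance under the null, no continuity correction. With p̄ = (p1 + p2)/2, s0 = √[2p̄(1 − p̄)/n] and s1 = √[(p1(1 − p1) + p2(1 − p2))/n]:

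power = Φ[(d − z·s0)/s1] + Φ[(−d − z·s0)/s1], where d = p1 − p2 and z = 1.977 for alpha 0.048.

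**Step 1: the plan's own figure.** For 50% versus 25% at alpha 0.05 and 80% power, n = 57.7, so 58 per group, and 58/0.10 = 580. Power with 58 per group is 80.2% at alpha 0.05 and 79.7% at 0.048. The SAP's arithmetic reproduces.

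**Step 2: the primary test as specified.** With the effect confined to GDM:

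- routine: p1 = g × 0.50 + (1 − g) × q
- early: p2 = g × 0.25 + (1 − g) × q
- difference: 0.25 × g, which is 0.025 at g = 10%

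Example with q = 20%: p1 = 0.05 + 0.18 = 0.230 and p2 = 0.025 + 0.18 = 0.205. Then p̄ = 0.2175 and s0 ≈ s1 ≈ 0.0242. The first term is Φ(−0.946) = 0.172 and the second is 0.001, so power is 17.3%.

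Power with 580 per arm, alpha 0.048:

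| Non-GDM rate q | GDM 6% | GDM 10% | GDM 20% |
|---|---|---|---|
| 0% | 39.9% | 60.4% | 89.6% |
| 5% | 16.7% | 33.4% | 75.6% |
| 10% | 12.1% | 24.2% | 64.7% |
| 20% | 9.3% | 17.3% | 51.2% |
| 30% | 8.3% | 14.8% | 44.3% |
| 40% | 7.9% | 13.6% | 40.7% |
| 50% | 7.8% | 13.2% | 39.3% |

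An exact binomial calculation of the chi-square > 3.91 rule agrees at 10% GDM: 61.2% at q = 0, 17.3% at q = 20%, 13.5% at q = 50%.

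**Step 3: what would give 80%.** With 580 per arm and q of 20, 30, 40 and 50%, GDM incidence would have to be 28.6, 30.9, 32.3 and 33.0%, all above the SAP's range.

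**Step 4: a higher event rate in women with GDM.** Still halved and still 10% GDM:

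- At 56%, the difference is 0.10 × 28 = 2.8 points and power is 15-20% for q of 20-50%.
- At 70% (assumed, to allow for the wider composite), it is 0.10 × 35 = 3.5 points and power is 22-29%. At 20% GDM this becomes 66-77%.

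**Step 5: what the trial can detect.** Absolute difference in all randomized women giving 80% power, 580 per arm, alpha 0.048:

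| Routine-arm rate | Difference | Risk ratio |
|---|---|---|
| 20% | 6.2 points | 0.69 |
| 30% | 7.3 points | 0.76 |
| 40% | 7.9 points | 0.80 |
| 50% | 8.2 points | 0.84 |

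**The case against.** Four points can be made for the plan.

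- **The premise is inferred.** The SAP never says the effect is confined to women with GDM. If early screening halved the composite in everyone, 580 per arm would give 97% power at an overall routine rate of 14% and more at higher rates. This stands as a condition on every percentage for the all-randomized test. But the documents neither propose nor justify such an effect, and the mismatch between the 80% and the test does not depend on it.
- **The non-GDM rate is assumed.** This is true, so the firmer statement is the ceiling: at 10% GDM and the SAP's 50% versus 25%, no non-GDM rate gives more than about 60%. With a 70% rate in women with GDM, power at a non-GDM rate of zero is 76%.
- **Favourable combinations exist.** At 20% GDM and a 70% rate in women with GDM, power is 86% at a non-GDM rate of 10% and 92% at 5%. These need the top of the incidence range and a low background rate together, and they are not the plan's own 10% and 50%.
- **The quoted sentence is literally true of 58 women with GDM, and the planned risk ratios with confidence intervals will show what a null result excludes.** Both are fair. What is missing is a planning figure for the primary test, and the sentence stands where that figure belongs.

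One further limit applies. The calculation uses the same GDM proportion in both arms, yet the early arm is tested twice: "In those who are not diagnosed with GDM at the early screen, repeat testing will be performed at 24-28 weeks". Diagnosed GDM may therefore differ between arms.

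**Conclusion.** The concern holds. The 80% is arithmetically right for a 58 versus 58 comparison that the SAP does not specify as its primary test, and no power is given for the test that is specified. This part needs no assumption.

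The size of the shortfall rests on two assumptions: no effect in women without GDM, and equal GDM incidence in the arms. At the planned 10% incidence and 50% versus 25%, power is at most about 60%. It is 13-17% if the non-GDM rate is 20-50%, a range the documents do not give. The planned effect is then 2.5 points overall, against the 6.2-8.2 points that 580 per arm can detect with 80% power.

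**What to change.** In SAP sections 3.1.3 and 3.2:

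1. Replace the 80% statement with the power of the all-randomized test: 580 per arm at alpha 0.048 gives 80% power for the differences in the Step 5 table. State which routine-arm rate is expected and its source; a pooled rate with both arms combined would serve.
2. State that a halving confined to women with GDM is about 2.5 points overall at 10% incidence, with power well below 80%. Give the assumed non-GDM rate beside any power figure.
3. State that conditional power shown to the DSMB uses the effect in all randomized women.
4. Keep the all-randomized comparison primary. A GDM-only comparison would match the 58 but would not be protected by randomization. As the SAP itself says, "The diagnosis of GDM will occur after patients in this study have been screened for GDM", and the timing of that screening is what differs between the arms.

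The cost is SAP wording only, with no extra patients and no change to endpoint or test. It does not raise the power; the stated power becomes much less favourable.
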